**Revision Chronology**

| GlaxoSmithKline Document Number  | Date | Version  |
|---|-------------|-----------------|
| 2012N140248_00  | 2015-SEP-30 | Original        |
| 2012N140248_01  | 2015-DEC-02 | Amendment No. 1 |
| 

• Deletion of compound numbers on the title page and the entering of “None”.

• Deletion of the development status on the title page and entering “NA”.

• Changing the study to an interventional study from non-interventional (Section 4).

• Deletion of the collection of race and ethnicity (Section 6.2).

   |             |                 |
| 2012N140248_02  | 2016-JAN-18 | Amendment No. 2 |
| 

• Clarification of digital rectal exam throughout the protocol.

• Addition of criteria for probable BPH (Study 4).

• Addition to concomitant medications - exclusion criteria (Section 5.2.).

• Addition of footnotes to Time and Events Table. (Section 6.1.).

• Deletion of text referring to GSK product. (Section 6.3.1.1. and Section 6.3.1.3.).

 |             |                 |

# 1. PROTOCOL SYNOPSIS FOR STUDY FDC116114

## Rationale

The rationale for developing an instrument to screen populations of men for lower urinary tract symptoms (LUTS) due to benign prostatic hyperplasia (BPH) is that it may help a General Practitioners (GP) to identify patients who may have BPH for further tests and improve the speed of referrals to specialists when this is appropriate. Symptomatic BPH is present in 40 – 60% of men over the age of 50 and prevalence rises with age. It is known that men with LUTS may be reluctant to discuss these symptoms with their GP, and that GPs do not routinely proactively ask about LUTS when men present for other complaints. As a result, many men with BPH present late with more severe symptoms. As a result up to 70% of men may have moderate to severe BPH at their initial diagnosis. The recent D-IMPACT study confirmed that GPs can accurately diagnose BPH in around 75% of men presenting with LUTS, using simple tests. A Benign Prostatic Enlargement (BPE)/Benign Prostatic Obstruction (BPO) screening tool which identifies LUTS probably due to BPH in men not yet presenting with LUTS would provide an opportunity to proactively assess men who do not present with LUTS. BPH is a progressive condition and identifying men at risk of progression is important to allow their treatment to be optimised. Furthermore the utility of the screening tool will be compared to the validated tool in wide clinical use, the International Prostate Symptom Score (IPSS).

## Objective(s)/Endpoint(s)

| Objectives  | Endpoints   |
|---|---|
| Primary  |   |
| To assess the utility of a BPE/BPO screening tool in conjunction with serum prostate specific antigen (PSA) in finding men confirmed to have BPH on full urologist assessment of diagnostic test results.   | Proportion of men that are confirmed to have BPH based on full urologist assessment of diagnostic test results among men with a positive result on the BPE/BPO screening tool (score $\geq 3$ ) and serum PSA $\geq 2$ ng/mL.   |
| Secondary  |   |
| 
 
To assess the utility of a BPE/BPO screening tool in conjunction with serum PSA in finding men with risk of BPH Progression on full urologist assessment of diagnostic test results.
 
To assess the utility of a BPE/BPO screening tool in finding men diagnosed with probable BPH as assessed by the GP.
 
Compare the utility of the BPE/BPO screening tool with the International Prostate Symptom Score (IPSS) screening tool.
 
 | 
 
Proportion of men that are confirmed to be a risk for BPH progression based upon full urologist assessment among men with a positive result on the BPE/BPO screening tool (score <math>\geq 3</math>) and serum PSA <math>\geq 2</math> ng/mL.
 
Proportion of men that are diagnosed with probable BPH as assessed by the GP among men with a positive result on the BPE/BPO screening tool (score <math>\geq 3</math>).
 
Agreement (using Kappa statistic for categories) between the BPE/BPO screening tool assessment (score <math>\geq 3</math>) and an IPSS score approach (score <math>\geq 8</math>) in selecting men to investigate for BPH).
 
 |
|  Probable BPH is the presumptive diagnosis of urinary tract obstruction from an enlarged prostate based on clinical symptoms and findings where urinary symptoms are not apparently related to any other cause.   |   |

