### **4.4. Design Justification**

The BPE/BPO screening tool has been developed using the currently recommended FDA guidelines ([Food and Drug Administration](#), 2009) for developing patient-completed questionnaires such as Patient Reported Outcomes. The tool to be used in this study in the General Practice setting has undergone validation in a urology setting to demonstrate the validity of the tool in populations with and without a definite diagnosis of BPH (GSK Study FDC116700). The FDC116700 study demonstrated that the most effective have been observed by screening patients with BPE/BPO items with a threshold score  $\geq 3$  and then testing such patients with PSA. With total PSA greater than or equal to 2 the combination screener/PSA shows a sensitivity of 83.8% and a specificity of 74.0%, with an accuracy of 80.1%.

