### **8.4.2. Primary Analyses**

The primary endpoint is defined as the proportion of men confirmed to have BPH based on full urologist diagnostic testing among men with a positive result on the BPE/BPO screening tool (score  $\geq 3$ ) and serum PSA  $\geq 2$  ng/mL. Primary endpoint summaries will be descriptively presented in terms of the calculated proportion, described below, and 95% confidence interval on the proportion. Formal hypothesis testing will not be conducted.

| Tool        | Proportion  | Numerator  | Denominator  |
|-------------|---|--|--|
| BPE/
BPO | BPH Diagnosis by Urologist based upon BPE/BPO screening tool (score $\geq 3$ ) and serum PSA $\geq 2$ ng/mL | Number of subjects diagnosed with BPH based on full urologist diagnostic testing | Number of subjects with a positive result on the BPE/BPO screening tool (score $\geq 3$ ) and serum PSA $\geq 2$ ng/mL and a BPH assessment by urologist |

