**7.1.2. Planned Primary Efficacy Statistical Analyses**

Primary Statistical Analyses			
Endpoint(s)			

 
Proportion of men that are confirmed to have BPH based on full Urologist assessment of diagnostic test results among men with a positive result on the BPE/BPO screening tool (score <math>\geq 3</math>) and serum PSA <math>\geq 2</math> ng/mL.
 
Primary endpoint summaries will be descriptively presented in terms of the calculated proportion, described below, and 95% confidence interval on the proportion. Formal hypothesis testing will not be conducted.
 
			
Tool	Proportion	Numerator	Denominator
BPE/BPO	BPH diagnosis by Urologist based upon BPE/BPO screening tool (score $\geq 3$ ) and serum PSA $\geq 2$ ng/mL.	Number of subjects diagnosed with BPH based upon a BPH assessment by Urologist.	Number of subjects with a positive result on the BPE/BPO screening tool (score $\geq 3$ ) and serum PSA $\geq 2$ ng/mL and a BPH assessment by Urologist.

 
Table 3 provides an overview of the planned summaries and primary efficacy analyses. A list of planned data displays is in Appendix 15: List of Data Displays.
 
			
Model Specification			

 
No models were used during the statistical analysis; proportions and confidence intervals were computed.
 
			
Model Checking & Diagnostics			

 
Not Applicable
 
			
Model Results Presentation			

 
Not Applicable
 
			
Sensitivity and Supportive Statistical Analyses			

 
Not Applicable
 
			

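### The primary endpoint is a positive predictive value: it shows how many referred men have BPH, not how many men with BPH the strategy finds, and neither a detection yield nor a paired comparison with IPSS is planned

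*Protocol*

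**What the plan says.** The synopsis words the primary objective thus: "To assess the utility of a BPE/BPO screening tool in conjunction with serum prostate specific antigen (PSA) in finding men confirmed to have BPH". Protocol 3 has it in nearly the same words. The endpoint beside it in the synopsis reads "Proportion of men that are confirmed to have BPH based on full urologist assessment of diagnostic test results among men with a positive result", where positive means BPE/BPO ≥3 together with PSA ≥2 ng/mL.

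In Protocol 8.4.2 the denominator is men with a BPE/BPO score of at least 3 who also have a serum PSA of at least 2 "ng/mL and a BPH assessment by urologist". SAP 7.1.2 matches it: "ng/mL and a BPH assessment by Urologist". The variant wording in the synopsis (Analysis), Protocol 8.1 and SAP 2.4 uses the GP's probable-BPH diagnosis in place of the PSA cut-off, but it too counts only positives.

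Who reaches the urologist:
- Men negative on both questionnaires are screen failures (Protocol 5.3).
- Enrolled men without probable BPH, which includes those with PSA <2, finish at the telephone call (Protocol 4.1).

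The secondary proportions (Protocol 8.4.3, SAP 8.1.2) are all conditional on a positive tool. The objective of comparing the tool's utility with IPSS is served by separate proportions for each tool and by kappa. SAP 7.1.2 and 8.1.2 list sensitivity and supportive analyses as not applicable.

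Protocol 4.4 supports the tool with an earlier study in a urology setting, FDC116700, where "the combination screener/PSA shows a sensitivity of 83.8% and a specificity of 74.0%, with an accuracy of 80.1" (the last figure is also a percentage). On prevalence, the synopsis rationale says that "Symptomatic BPH is present in 40 – 60% of men over the age of 50".

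**The concern.** A screening strategy can be useful in two ways: the men it refers mostly have the disease, and it picks up a good share of those who have it. The objective speaks of finding men, which is the second. The endpoint measures only the first.

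A PPV has two properties that matter here. It is the same for any two tools with the same ratio of sensitivity to (1 − specificity), however many cases each misses. It also changes with prevalence when the tool itself does not change.

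The comparison with IPSS has the same gap. Two separate PPVs show which tool's referrals are more often confirmed. Kappa shows how often the questionnaires agree. Neither shows which tool finds more confirmed cases in the same men.

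**Working it through.** **The plan's own precision.** Half-width = 1.96 × √(0.5 × 0.5 / n).
- n = 300: 0.0566
- n = 500: 0.0438
- n = 700: 0.0370

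These match the ±0.057, ±0.044 and ±0.037 in Protocol 8.2. Also 33% × 1,500 = 495, the plan's approximately 500. The sample size is correct for the proportion as defined.

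**Prevalence in the earlier study.** Inputs from Protocol 4.4: sensitivity 0.838, specificity 0.740, accuracy 0.801.
- 0.838p + 0.740(1 − p) = 0.801, so p = 0.061 / 0.098 = 0.622.
- PPV there = 0.838 × 0.622 / (0.838 × 0.622 + 0.26 × 0.378) = 0.842.

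**PPV and cases found.** PPV = Se·q / (Se·q + (1 − Sp)(1 − q)), where q is prevalence. The quoted figures give a positive likelihood ratio of 0.838 / 0.26 = 3.22. For contrast, assume a tool with sensitivity 0.20 and the same ratio; its specificity is 1 − 0.20 / 3.22 = 0.938. In 1,500 men:

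| Prevalence | PPV, either tool | Cases present | Found, 83.8%/74.0% | Found, assumed 20%/93.8% |
|---|---|---|---|---|
| 40% | 68.2% | 600 | 503 | 120 |
| 50% | 76.3% | 750 | 629 | 150 |
| 60% | 82.9% | 900 | 754 | 180 |

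The 40–60% range is the protocol's, for men over 50 in general. Exclusion criteria 1 and 2 remove men already investigated or treated for BPH or prostate-related LUTS, so it may be too high here. At an assumed 20%, PPV = 0.1676 / (0.1676 + 0.208) = 0.446.

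**Check against the 33% referral figure.** If 83.8%/74.0% carried over unchanged:
- 0.838p + 0.26(1 − p) = 0.33, so p = 0.07 / 0.578 = 0.121.
- PPV = 0.838 × 0.121 / 0.33 = 0.31.

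This is rough. Protocol 8.2 includes IPSS-only positives in the 33%, and the GP's judgement also intervenes. It shows that 76% is not what the plan's own figures predict.

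**What the design can estimate.** Detection yield (confirmed cases per man screened) equals sensitivity × prevalence, so it also depends on prevalence: 0.838 × 0.12 and 0.20 × 0.50 both give about 0.10. The paired ratio does not have this weakness. Among men with PSA ≥2 and urologist-confirmed BPH, let a be positive on both tools, b on BPE/BPO only and c on IPSS only. Then (a + b) / (a + c) is the relative detection of the two strategies, because the unknown total of cases cancels. It is estimable because IPSS-only positives are also referred.

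**The case against.** The strongest reply is that objective and endpoint stand side by side in the tables, so the endpoint openly defines utility. The stated purpose is to help GPs choose men for further tests and referral, and the share of referred men who are confirmed measures that directly. There is no hypothesis test or success threshold. This stands: a PPV is a legitimate measure.

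Second, most of the counts will be reported. The accountability tables (SAP 6.2, Tables 1.1 and 1.6) give men screened, evaluable, with PSA ≥2, GP-positive and urologist-confirmed. Table 2.1 cross-classifies the tools in all screened men, and Protocol 4.1 gives the tools only after the other criteria are met. Table 2.13 supplies the numerator. This also stands. What is missing is a pre-specified ratio and its CI. The confirmed counts in the accountability tables are also defined by GP = Yes rather than by PSA ≥2.

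Three stronger readings are tempting, and the documents do not support them:
- **That a tool finding few cases and one finding most would look identical.** Only the expected proportion is equal. At 50% prevalence the two illustrative tools flag about 824 and 197 of 1,500 men, with half-widths of about 2.9 and 5.9 points, and the second would visibly miss the planned 500 referrals.
- **That reporting yield would settle how much BPH is found.** Yield is sensitivity × prevalence and cannot separate the two.
- **That the trial sets its result against FDC116700.** No section plans this. The caution is for a reader who does so.

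**Conclusion.** The concern holds as a limit on what can be concluded. The primary proportion is valid as a PPV in men seen by the urologist. It does not measure detection, and the design cannot estimate absolute sensitivity or specificity because double-negative men and men with PSA <2 have no urologist assessment. The comparison with IPSS lacks a measure of which tool finds more cases in the same men.

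On size, prevalence alone moves the PPV from 45% to 83% across 20–60% at fixed sensitivity and specificity, and a fourfold difference in cases found can leave the expected proportion unchanged. That rests on applying urology-setting accuracy to general practice, on assumed prevalences, on an invented comparison tool, and on ignoring GP judgement and refusals. The algebra does not depend on these assumptions; the percentages do. This is an inexpensive improvement and does not invalidate the primary analysis.

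**What to change.** In SAP 2.2 and 8.1.2, add with 95% CIs:
- **Detection yield.** Numerator: men with BPE/BPO ≥3, PSA ≥2 and urologist BPH = Yes. Denominator: all men who met the other criteria and completed both tools. Give the number screened per confirmed case, and the same for IPSS ≥8.
- **Paired ratio.** (a + b) / (a + c) as defined above. A CI on the log scale can use the standard error √[(b + c) / ((a + b)(a + c))].
- **Unverified referrals.** Show GP-positive men without a urologist assessment separately, and bound the yield by counting them as none confirmed and then as all confirmed.

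In the protocol objective (synopsis and section 3), SAP 2.2 and the planned conclusion, describe the primary result as a positive predictive value of BPE/BPO ≥3 plus PSA ≥2 in previously untreated men in general practice. State that absolute sensitivity and specificity are not estimated, that yield also depends on prevalence, and that the result is not directly comparable with the FDC116700 figures.

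The cost is one or two tables from data already collected, with no extra patients or tests. The objective is protocol text, so its rewording needs a protocol amendment. Changing the SAP alone would create a contradiction, and SAP 2.1, which declares no changes from the protocol, would also need updating. The claim becomes narrower.

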## Overall Design

- This study will evaluate the utility of the Benign Prostatic Enlargement (BPE)/ Benign Prostatic Obstruction (BPO) screening tool in a general practice setting where the results of this screening tool will be used for further investigation. Therefore in this study, all men testing positive on the BPE/BPO screening tool (score  $\geq 3$ ) tool or on the IPSS (score  $\geq 8$ ) will be enrolled and offered a prostate specific antigen (PSA) test and urinalysis to establish a diagnosis of probable benign prostatic hyperplasia (BPH) (Part I – Visit 1). The General Practitioner (GP) may perform a DRE (digital rectal examination), however the DRE will be repeated by the urologist to confirm the diagnosis and to rule out an abnormality suggesting prostate cancer. The GP will make a diagnosis of probable BPH based upon screening results and lab tests which suggest that they are related to BPH and not other causes of such symptoms.
- The GP will phone the subject to report yes or no for probable BPH Part II (Visit 2). If the subject has probable BPH, the GP will schedule the subject for Visit 3 with a urologist. If the subject does not have probable BPH, then the subject has completed the study.
- Subjects that proceed to Part II (Visit 3) will be scheduled for a urology assessment performed by a urologist. This assessment includes a DRE and a brief physical exam and review of the PSA test, for a confirmatory diagnosis of BPH and estimation of risk of progression of BPH.

## Treatment Arms and Duration

- Approximately 1,500 males presenting to a GP with a primary complaint other than LUTS will be screened for probable BPH to yield 500 subjects being referred to a urologist.
- The duration of the study will be 1 week ( $\pm 4$  days) and up to 6 weeks to allow for GP and urologist visit scheduling.
- There is no study drug in this study.

## Type and Number of Subjects

- Approximately 1,500 males  $\geq 50$  years presenting to a GP for reasons unrelated to this study will be screened for probable BPH to yield 500 subjects being referred to a urologist.

## Analysis

- The primary endpoint is defined as the proportion of men that are confirmed to have BPH based on full urologist assessment of diagnostic test results among men with a positive result on the BPE/BPO screening tool and probable BPH diagnosis as assessed by the GP. For this proportion, the numerator is number of subjects diagnosed with BPH by a urologist; denominator is number of subjects with a positive result on the BPE/BPO screening tool and a probable BPH assessment by

the GP and a BPH assessment by the urologist. The 95% confidence interval for this proportion will be presented.

- Sufficient general practice centres (50 consecutive men per centre) in various markets will be recruited to administer the BPE/BPO screening tool to 1,500 men (using protocol defined criteria) presenting to clinic for reasons unrelated to the study. It is expected that 33% of the 1,500 presenting (or approximately 500) will have a positive result on the BPE/BPO screening tool and a probable BPH assessment by GP and thus will be assessed by a urologist.
- Due to the design of the study and types of endpoints incorporated, ‘observed cases’ will be summarized for a subset of subjects in study Parts I and II. There will be no imputations for missing data or for discontinued subjects.
- An interim analysis is not planned for this study.

## 2. INTRODUCTION

- This study will evaluate the utility of the Benign Prostatic Enlargement (BPE)/ Benign Prostatic Obstruction (BPO) screening tool in a general practice setting where the results of the BPE/BPO screening tool will be used for further investigation. Therefore in this study, all men testing positive with the BPE/BPO tool (score  $\geq 3$ ) and/or on the IPSS (score  $\geq 8$ ) will be enrolled and offered a prostate specific antigen (PSA) test and urinalysis to help establish a diagnosis of probable benign prostatic hyperplasia (BPH) (Part I – Visit 1). The GP may perform a DRE, however the DRE will be repeated by the urologist to confirm the diagnosis and to rule out an abnormality suggesting prostate cancer.
- The GP will phone the subject to report yes or no for probable benign prostatic hyperplasia (BPH) Part II (Visit 2). If the subject has probable BPH, the GP will schedule the subject for Visit 3 with a urologist. If the subject does not have probable BPH, then the subject has completed the study.
- For those subjects that proceed to Part II (Visit 3) they will be scheduled for a urology assessment performed by a urologist. This assessment includes DRE and a brief physical exam with review of the PSA test, for a confirmatory diagnosis of BPH and estimation of risk of progression of BPH.

### 2.1. Study Rationale

The rationale for developing an instrument to screen populations of men for lower urinary tract symptoms (LUTS) due to BPH is that it may help a GP to identify patients who may have BPH for further tests and improve the speed of referrals to specialists when this is appropriate. Symptomatic BPH is present in 40 – 60% of men over the age of 50 and prevalence rises with age (Emberton, 2003). It is known that men with lower urinary tract symptoms (LUTS) may be reluctant to discuss these symptoms with their GP, and that GPs do not routinely proactively ask about LUTS when men present for other complaints. As a result, many men with BPH present late with more severe symptoms. As a result, up to 70% of men may have moderate to severe BPH at their initial diagnosis. The recent D-IMPACT study confirmed that GPs can accurately

diagnose BPH in around 75% of men presenting with LUTS, using simple tests (Carballido, 2011). A simple screening tool which identifies LUTS probably due to BPH in men not yet presenting with LUTS would provide an opportunity to proactively identify and potentially treat men who do not present with LUTS as their primary complaint. It is important to identify BPH early. BPH is a progressive condition and identifying men at risk of progression is important to allow their treatment to be optimised (Fitzpatrick, 2006). Furthermore the utility of screening tool will be compared to a validated tool in wide clinical use, the International Prostate Symptom Score (IPSS).

## 2.2. Brief Background

Symptomatic BPH is present in 40 – 60% of men over the age of 50 and prevalence rises with age (Emberton, 2003). It is known that men with LUTS may be reluctant to consult, and that GPs do not proactively ask about LUTS when men present for other co-morbidities. As a result many men present late, and up to 70% of men may have moderate to severe BPH at diagnosis. Some of these men may have an increased prostate volume (>30 cc) and a prostate specific antigen (PSA)  $\geq 1.5$  ng/mL, and therefore be at risk of progression (Roehrborn, 2007). Under European Association of Urology (EAU) guidelines, these men may be suitable for treatments targeted to the underlying cause of the disease.

The International Prostate Symptom Score (IPSS) score is well validated as a tool to assess the severity of LUTS symptoms, and has similarly been used for assessing symptomatic efficacy of treatments for BPH (Roehrborn, 2008). Nevertheless this tool was not developed as a diagnostic tool for BPH. Furthermore, GPs are reluctant to use the IPSS because it takes time away from other problems and extends the patient visit time and may require other staff to implement. An abbreviated diagnostic tool would therefore assist the GP in diagnosis and timely referral to a urologist.

A screening tool which identifies LUTS probably due to BPH in men presenting for reasons unrelated to the study would provide an opportunity to proactively assess men who may not consider presenting with these symptoms. BPH is a progressive condition and identifying men at risk of progression is important to allow their treatment to be optimised (Fitzpatrick, 2006).

